[name], Professor of Medicine and Bioengineering, Pulmonary, Allergy and Critical Care Medicine, University of Pittsburgh, [name] [contact] [contact].

Independent Medical Monitor: [name] NHLBI (E) [name], [name]

Collaborating Pharmaceutical Company:

APT Pharmaceuticals, Inc., [name]

| // | | Number | Sex | Age range |
|--|----------|---------------------------------------|--------|-----------|
| Hematopoietic stem cell transplant recipients (g | group A) | Screen up to 50 to get up to 39 | Either | 10-80 |
| | | Screen up to | | |
| | | 50 to get | | |
| Lung transplant recipients (Group B) | | up to 39 | either | 10-80 |
| (No longer enrolling) | | Screen up to | | |
| | | 100 to get | | |
| Total subjects | | up to 78 | either | 10-80 |
| Project involves ionizing radiation? | Yes | | | |
| Off site project? | No | | | |
| Multi-institutional project? | No | | | |
| DSMB involved | Yes | | | |

Precis

Bronchiolitis Obliterans (BO) is an obstructive lung disease that can affect individuals that have undergone a lung or hematopoietic stem cell transplant. BO has been studied most extensively in lung transplant recipients, where it is considered to represent chronic lung rejection. It is the leading cause of death after lung transplant, with mortality rates up to 55%. In hematopoietic stem cell transplantation, BO is thought to be a manifestation of chronic graft-vs-host disease (GVHD). Up to 45% of patients undergoing hematopoietic stem cell transplantation at the NHLBI develop a decline in pulmonary function. Conventional therapy for patients who develop BO consists of augmentation of systemic immunosuppressants. Systemic immunosuppression has limited efficacy for BO and is associated with deleterious consequences including increased risk of infections and decreased graft-versus tumor/leukemia effects.

Recently, cyclosporine inhalation solution (CIS) in solution with propylene glycol has been shown to improve overall survival and chronic rejection-free survival in lung transplant patients.⁽⁸⁾ These findings suggest targeted delivery of immunosuppressive therapy to the diseased organ warrants further investigation as this may minimize the morbidity associated with systemic immunosuppression. However, there currently exists limited data regarding the overall efficacy of inhaled cyclosporine to treat established BO following lung transplantation. Furthermore, inhaled cyclosporine has not been studied in the treatment of BO following hematopoietic stem cell transplantation.

Here, we propose to evaluate the safety, efficacy, and pharmacodynamics of inhaled cyclosporine for the treatment of BO. Two distinct patient populations will be offered enrollment in this protocol: hematopoietic transplant recipients with BO (group A) and lung transplant recipients with BO (group B). Study participants will receive CIS at an initial dose of 150mg, three times weekly. Patients will undergo dose titration to a maximum dose of 300mg, three times weekly. Drug deposition and pharmacokinetic analyses will be performed at the initiation of treatment. Clinical parameters, including pulmonary function tests, will be measured in addition to laboratory markers of the anti-inflammatory response to CIS. Adverse events associated with treatment will be recorded.

The primary objective is to 1) assess the safety and efficacy of inhaled cyclosporine as a new therapy in hematopoietic transplant patients and lung transplant patients with established BO. Additionally, we seek to promote a better understanding of the pathogenesis of BO in these two transplant groups and to assess the anti-inflammatory effects of inhaled cyclosporine in patients that develop this complication.

The *primary endpoint* of each study group is the best response, FEV₁ improvement or stabilization from study baseline at week 18 for two successive measures, at least 1 week apart, no more than 2 weeks apart. *Secondary endpoints* include the toxicity profile as measured by CTCAE criteria (safety), the study of pharmacokinetics and lung deposition characteristics of inhaled cyclosporine, improvement in high resolution chest CT images, results of peripheral blood and bronchoalveolar cytokine arrays to assess secondary markers of inflammation, and functional capacity measurements using a six-minute walk test.

1.0 OBJECTIVES

1.1 Primary objective:

To assess the safety and efficacy of inhaled aerosolized cyclosporine A solution in hematopoietic (group A) and lung transplant patients (group B) with bronchiolitis obliterans (BO) or BO syndrome (BOS). As of Amendment M, lung transplant patients are no longer being enrolled on this protocol.

1.2 Secondary Objectives

- To evaluate the lung deposition and pharmacokinetics of this CSA preparation
- To investigate the inflammatory pathways that lead to the development of BO
- To ascertain the anti-inflammatory effects of this CSA preparation ex vivo and in vivo

2.0 BACKGROUND

2.1 Introduction

After the first year post lung transplant, BO is the leading cause of death, accounting for 26% of all deaths between post transplant years 1 and 3⁽¹⁾. Annually, approximately 15,000 allogeneic hematopoietic stem cell transplants are performed. BO as a manifestation of chronic graft-vs.-host disease (GVHD) can also occur after hematopoietic stem cell transplantation. Up to 45% of patients undergoing hematopoietic stem cell transplantation at the NHLBI develop a decline in pulmonary function, with a significant proportion of these patients being diagnosed with BO⁽²⁾. Although similarities and differences in the pathogenesis of BO following lung and hematopoietic stem cell transplantations and are treated similarly with increased doses of systemic immunosuppressants. The current treatment for BO is inadequate and involves increasing systemic immunosuppression or immune-modulating therapies, which are of marginal efficacy.

2.2 Hematopoietic Transplant and BO / BOS

Hematopoietic stem cell transplant is an established therapy for the treatment of many lifethreatening diseases. However, there are many life-long complications associated with this treatment, especially lung disease. Pulmonary dysfunction after hematopoietic stem cell transplant has been well documented, and is one of the most frequent complications seen after transplant ^(2, 3, 4). The incidence of BO after hematopoietic transplant has been estimated between 5 and 60% ^(4, 10). The underlying pathophysiology is not completely understood, but it is thought that BO represents a form of chronic GVHD, with the lung epithelium serving as a target for immune-mediated injury induced by transplanted donor T lymphocytes ⁽⁵⁾. In concert with this proposed mechanism is the observation that GVHD is the greatest risk factor for the development of BO after stem cell transplant ⁽⁴⁾. This is also supported by the very low incidence of BO occurring after autologous stem cell transplant. It has been proposed that additional factors may have a role in the development of BO. Other factors may include recurrent aspiration due to GVHD induced esophagitis, infection, HLA mismatched transplant, use of busulfan or methotrexate, or lung disease prior to transplant ^(3, 4).

2.3 Lung transplant and BO / BOS

Bronchiolitis obliterans is the characteristic lesion seen on histology in chronic rejection after lung transplant. It is estimated that 50% of lung transplant recipients will develop BOS within five years of transplantation, with mortality rates upwards of 55% ^(10, 8). The pathogenesis of BOS development

after lung transplant is thought to have immune and non-immune facets. It has been postulated that airway inflammation and epithelial cell injury result in a disordered repair process that leads to the fibroproliferative obstruction of the small airways. The initial injury may result from allo-immune or immune-independent factors or both, but have a common final pathway, BO. Various immune mediated risk factors, which have been proposed as inciting events include: increased HLA mismatching, acute rejection, and lymphocytic bronchitis and bronchiolitis in the absence of infection. Non-immune mediated risk factors include chronic aspiration, infection, especially with CMV, and ischemic graft injury ^(6,10).

2.4 BO clinical findings and diagnosis

BO is an obstructive lung disease of the small airways. Patients may present with cough, dyspnea, wheezing, or may be asymptomatic at the time of diagnosis. Cough is present in 60-100% of patients and dyspnea in 50-70%⁽³⁾. In patients who have received a hematopoietic stem cell transplant, signs and symptoms of chronic graft versus host disease (GVHD) affecting other organs are often present.

The gold standard for the diagnosis of BO is histologic. On histology, there is fibrous proliferation affecting the small airways due to injury and inflammation of the epithelial cells. However, histologic evidence of disease is often difficult to obtain due to the patchy nature of the small airway involvement. As such, a set of clinical diagnostic criteria has been proposed by the NIH working group ⁽⁷⁾. When histology is not available, the term Bronchiolitis Obliterans Syndrome (BOS) is used. The diagnostic criteria for bronchiolitis obliterans syndrome is largely based on the presence of obstructive pattern pulmonary function tests with exclusion of other causes of airway obstruction such as asthma, infection or emphysema.

Criteria for the diagnosis of BOS, as proposed by the NIH working group, are met when all of the following are met:

- FEV_1/FVC less than 0.7 and a FEV_1 less than 75% predicted
- Evidence of air trapping on high-resolution chest CT or residual volume $\geq 120\%$
- Absence of infection in the respiratory tract
- One or more manifestations of chronic GVHD in another organ system
- A 10% decline from pre-transplant baseline in the FEV_1 and one of the following: FEV1/FVC less than 0.7, evidence of air trapping on CT or residual volume $\ge 120\%$

It is generally thought that this definition is too restrictive, and it has on more than one occasion excluded patients with biopsy proven BO. As such, in this study we will require for diagnosis of BOS an FEV₁ less than 75% predicted, absence of infection or other causative etiology, a 10% decline from pre-transplant baseline in the FEV₁ and one of the following: FEV1/FVC less than 0.7, evidence of air trapping on CT or residual volume \geq 120%, or in hematopoietic transplant recipients at least one other manifestation of cGVHD involving another organ system. In lung transplant recipients, the same criteria will be used, but the FEV₁ decline required will be greater than 20% compared to best post-transplant measurement.

For a determination of baseline values and diagnosis of BOS, FEV_1 measurements will be determined by the average of 2 sequential measurements taken at least 3 weeks apart up to 6 months apart. Patients can be on a bronchodilator; however, its use will be suspended during pulmonary function testing.

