5.0 ELIGIBILITY ASSESSMENT

5.1 Inclusion criteria

5.1.1 History of

- Hematopoietic stem cell transplant recipients at least 99 days post transplant (Group A)
- **5.1.2** Biopsy proven bronchiolitis obliterans (confirmed by NIH pathology department) or Bronchiolitis Obliterans Syndrome (BOS) as defined by:
 - $FEV_1 < 75\%$ predicted and
 - No evidence of pulmonary infection as a causative etiology to lung dysfunction or other causative etiology and
 - Decline in FEV₁ (The FEV₁ values used to determine BOS will be the average of 2 measurements of FEV₁ taken sequentially at least 3 weeks apart up to 6 months apart) compared to pre-transplant baseline for Group A.
 - For hematopoietic transplant patients, FEV₁ must have declined >10% from pretransplant baseline (group A)
 - And one of the following:
 - \circ FEV₁/FVC < 0.7
 - Air trapping seen on CT scan or RV≥120% predicted
 - Evidence of cGVHD affecting at least one other organ system (group A)
- 5.1.3 Age 10-80 years
- **5.1.4** Progressive disease or stable disease (active BOS, stable by FEV₁ criteria) on immunosuppressants at study entry
- **5.1.5** *Progressive disease at study entry:* Diagnosis of BO or BOS with evidence of a progressive decline in FEV₁. A documented decline (≥10%) in FEV₁ has occurred within 18 weeks (minimum documentation of 3 weeks) preceding study enrollment.
- **5.1.6** *Stable disease at study entry:* Diagnosis of BO or BOS on immunosuppressive therapy with evidence of stable disease (active BOS, stable by FEV₁ criteria), as documented by a stable FEV₁ (increase <5% and decrease <10%) within 18 weeks (minimum documentation of 3 weeks) preceding study enrollment.
- **5.1.7** Subjects on calcineurin inhibitors at study entry will be required to be on a stable dose of the calcineurin inhibitor for 4 weeks prior to study enrollment.

Prior to Amendment M, patients with lung transplant –associated BOS were eligible for the trial.

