6.2.3 Permitted Concomitant Medications

Post Transplant Medications: Subjects that require an increase in existing immunosuppressive meds by 25% due to worsening BOS symptoms (sustained for 3 weeks, excluding adjustments made for target drug levels) or need addition of new immunosuppressive therapies (sustained for 3 weeks), above baseline levels, due to worsening lung disease or BOS symptoms after week 9 will be categorized as treatment failures. However, if the increase or addition of new immunosuppressive therapies is for GVHD not involving the lung or to maintain baseline drug levels, this data will be captured and the subject will continue on study. Efforts will be made to make no changes in existing medical therapies other than tapering immunosuppressants in subjects who have PFTs showing stable or improved pulmonary function.

Systemic immunosuppressants will be tapered beginning at week 6, if subjects have an improvement or stabilization of FEV_1 compared to study baseline values, at the discretion of the PI, taking into account the subject's other manifestations of GVHD. Attempts will be made to taper prednisone first, before other systemic immunosuppressants. Prednisone will be decreased by 25% at the first taper. Subsequent tapers will be at the discretion of the PI. Lung transplant recipients will not have systemic immunosuppressants tapered.

Subjects that have improvement or stabilization of FEV_1 , are not on prednisone, and are only on calcineurin inhibitors, will have their steady state calcineurin inhibitor (systemic cyclosporine or tacrolimus) dose tapered at the discretion of the PI. The calcineurin inhibitor dose will be decreased by 25% at the first taper. Subsequent tapers will be at the discretion of the PI.

Lung Infection Prophylaxis:

Lung infection prophylaxis will be at the discretion of the PI, taking into account the patient's other concomitant medications and medical history. The following are guidelines:

- For PCP pneumonia prophylaxis, subjects will take Bactrim, one double strength tablet (800/160mg) orally three times weekly or aerosolized pentamidine 300mg every four weeks by inhalation.
- For antiviral prophylaxis, subjects will receive acyclovir 800 mg twice daily. Pediatric subjects less than 40kgs will receive acyclovir 20mg/kg po twice daily to a maximum dose of 800mg twice daily.

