7.0 STUDY ASSESSMENTS

7.1 Screening Evaluation (Screening will be done under protocol 97-H-0041 and will be used to establish eligibility and baseline status)

- History and Physical with emphasis on symptom assessment
- ECOG
- Review of concomitant medications
- Vital signs
- CBC with differential
- Acute Care, Mineral and Hepatic Panels
- Serum Beta- HCG in female subjects
- When applicable (i.e. on oral CSA), a CSA trough level
- Pulmonary Function tests
- Forced Spirometry
 - Slow Spirometry
 - Lung volumes with nitrogen washout

- Single Breath Diffusion
- Exhaled Nitric Oxide (subset of subjects)
- Six minute walk test
- EKG
- High Resolution Chest CT (HRCT)
- Determination of baseline status
 - Progressive disease at study entry
 - Diagnosis of BO or BOS with evidence of a progressive decline in FEV₁.
 Documented decline (≥10%) in FEV₁ has occurred within 18 weeks (minimum documentation of 3 weeks) preceding study enrollment
 - Stable disease (active BOS, stable by FEV₁ criteria) at study entry on immunosuppressants
 - Diagnosis of BO or BOS on immunosuppressive therapy with evidence of stable disease (active BOS, stable by FEV₁ criteria), as documented by a stable FEV₁ (increase <5% and decrease <10%) within 18 weeks (minimum documentation of 3 weeks) preceding study enrollment

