10.0 BIOSTATISTICAL CONSIDERATIONS

10.1 Primary and secondary endpoints

The *primary objective* is to assess the safety and efficacy of inhaled aerosolized cyclosporine A solution in hematopoietic (group A) and lung transplant patients (group B) with bronchiolitis obliterans (BO) or BO syndrome (BOS). The *primary endpoint* of each study group is FEV_1 improvement or stabilization from study baseline at week 18 for two successive measures, at least 1 week apart, no more than two weeks apart.

Criteria for response:

For subjects with progressive disease at study entry, (subjects with a documented decline ($\geq 10\%$) in FEV₁ within 18 weeks of study enrollment), improvement in BO is defined as an FEV₁ increase $\geq 10\%$ compared to baseline and stabilization of BO is defined as less than 10% increase to less than 10% decline in FEV₁ as compared to baseline.

For subjects with stable disease (active BOS, stable by FEV_1 criteria) at study entry (a stable FEV_1 , increase < 5% and decrease < 10% within the 18 weeks preceding study enrollment), improvement in BO is defined as an FEV_1 increase $\ge 10\%$ compared to baseline and stabilization of BO is defined as less than 10% increase to less than 10% decline in FEV_1 with a minimum 25% decrease in the dose of one or more systemic immunosuppressive drugs(assessed at week 18, sustained for 3 weeks, excluding adjustments made for target drug levels) while being treated with CIS. Subjects with stable BO at study entry that have less than a 10% increase to less than a 10% decline in FEV_1 as compared to baseline that have no reduction in systemic immunosuppression while receiving CIS will be considered non-responders. Response will require a confirmatory PFT result at least 1 week after 18 week assessment. The average of these two measurements will be used for assessment of response.

The treatment will be considered successful in each cohort if there is a more than 30% improvement or stabilization. Adverse events associated with the treatment will also be assessed. (Please see the table below)

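### Does the unnamed study baseline in section 10.1 charge FEV₁ lost before the first dose to inhaled cyclosporine?

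*Combined protocol and SAP*

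**What the plan says.** Section 10.1 defines the primary endpoint as FEV₁ "improvement or stabilization from study baseline at week 18 for two successive measures". The end value is fully specified: the mean of the week 18 test and its confirmatory test. The starting value is called study baseline, and no reading is named. A decline of 10% or more is non-response. In subjects who enter with progressive disease, any smaller change counts as response. Subjects who enter stable and stay within 10% respond only if systemic immunosuppression has been cut by at least 25%; those "that have no reduction in systemic immunosuppression while receiving CIS will be considered non-responders".

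The only numerical rule on baseline is in section 2.4: "For a determination of baseline values and diagnosis of BOS, FEV_1 measurements will be determined by the average of 2 sequential measurements taken" 3 weeks to 6 months apart. It follows diagnostic criteria that include "absence of infection or other causative etiology, a 10% decline from pre-transplant baseline in the" FEV₁. Section 5.1.2 gives the same average for the values that determine BOS: "taken sequentially at least 3 weeks apart up to 6 months apart) compared to pre-transplant baseline for Group A". Progressive entry under 5.1.5 needs a fall of at least 10% that "has occurred within 18 weeks (minimum documentation of 3 weeks) preceding study enrollment".

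Under section 7.1 the screening tests "will be used to establish eligibility and baseline status", and 7.3 lets the principal investigator (PI) repeat lung function at week 1. Section 6.2.3 also uses the term, for tapering when FEV₁ is stable or better "compared to study baseline values, at the discretion of the PI", and names no reading there either.

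**The concern.** The endpoint is a binary call at a 10% cut, so the denominator matters. A pair of readings 3 to 18 weeks apart that documents progressive entry also fits the 3-week to 6-month averaging window in 2.4. One pair could therefore serve both purposes. Its mean lies above FEV₁ at the start of treatment, and loss that preceded the first dose would be counted against the drug.

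The same FEV₁ course could then be response or non-response depending on a reading the plan does not name. The trial is single-arm and open-label, and one subject can turn the decision: 6 against 7 responders of 19 at stage 1, and 16 against 17 of 39 at the end. Halting decline is the effect sought in progressive-entry subjects, and they are the ones exposed. An unnamed denominator could also be settled after results are known.

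**Working it through.** **The plan's design figure.** Exact binomial calculation of the section 10.2 rule (stop at 6 or fewer of 19; success at 17 or more of 39) gives type I error 0.0455 at a response rate of 0.3 and power 0.8036 at 0.5. A minimax search returns the same rule, so 39 per group reproduces. None of this depends on the baseline; only the scoring of individual subjects does.

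**A flat course against the averaged pair.** Set the earlier reading to 1 and the entry fall to d. The later reading is 1 − d and the pair mean is 1 − d/2. If FEV₁ then stays at 1 − d, the change from baseline is (1 − d)/(1 − d/2) − 1.

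- d = 10%: 0.90/0.95 − 1 = −5.3%
- d = 15%: 0.85/0.925 − 1 = −8.1%
- d = 20%: 0.80/0.90 − 1 = −11.1%

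The cut is reached when 1 − d = 0.9(1 − d/2), so 0.10 = 0.55d and d = 2/11 = 18.2%. Against a pre-dose reading taken after the fall, every one of these is 0%. If both averaged readings follow the fall, there is no offset.

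**Stable entry.** With prior change g between −10% and +5%, the offset (1 + g)/(1 + g/2) − 1 runs from −5.3% to +2.4%, so a flat course stays inside the band. The rise from entry FEV₁ needed for improvement, 1.1(1 + g/2)/(1 + g) − 1, is 16.1% at g = −10%, 10.0% at g = 0 and 7.4% at g = +5%.

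**With measurement error.** The documents give no within-subject coefficient of variation, so 3%, 5% and 7% are assumed. Subjects are simulated with lognormal error, an observed fall of at least 10%, and an endpoint that averages weeks 18 and 19. Share of truly flat subjects scored as responders with the straddling average:

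| True fall | CV 3% | CV 5% | CV 7% |
|---|---|---|---|
| 10% | 95% | 84% | 76% |
| 15% | 75% | 66% | 61% |
| 20% | 34% | 40% | 43% |

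With the last pre-dose reading the share is 95–100% at a true fall of 15% and 93–100% at 20%. With the mean of screening and a week-1 repeat it is 96–100% and 95–100%.

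**The opposite error.** Take a subject who truly loses a further 15% on treatment, after a true entry fall of 10–15%. Chance of being scored a responder, over the same CVs:

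- straddling average: 0–5%
- mean of screening and week-1 repeat: 3–29% (3–21% for two readings not selected for a fall)
- last reading alone: 7–41% (6–26% for one unselected reading)

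A baseline that includes the low qualifying reading is subject to regression to the mean, which favours the drug. As an illustration only, if this moved the true null response rate from 0.30 to 0.31, 0.32 or 0.33, type I error would go from 4.6% to 6.0%, 7.9% or 10.1%.

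**Which reading the text supports.** Section 2.4 is background and its sentence follows criteria in which baseline means the pre-transplant value. Section 5.1.2, the operative criterion, ties the average to determining BOS. Section 10.1 does not cite 2.4. Sections 7.1 and 8.0 place baseline status in the evaluations before study treatment, and 8.1 refers peak-flow decline to a pre-treatment value. Together they support a pre-dose value.

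**The case for a change.** The best case for a change is that section 2.4 pairs baseline values with diagnosis, so an analyst could apply its average to the endpoint in good faith. Sections 7.1, 8.0 and 8.1 lean towards a pre-dose value without defining one, and the week-1 repeat in 7.3 has no stated role. Naming the readings would cost one sentence.

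Much of this stands. The text available does leave the term open, and the choice between one and two pre-dose readings is not neutral. For a subject who loses a further 15% after a true fall of 10%, it moves the chance of a response call from 5/18/29% (two readings) to 11/30/41% (last reading) at CVs of 3/5/7%.

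What does not stand is the step from silence to a biased endpoint. That needs progressive entry, section 2.4 governing section 10.1, and a pair that straddles the fall; a flat course becomes certain non-response, before measurement error, only if the fall is also at least 18.2%. Nor is there a clearly better rule to write in. Fixing a post-fall pre-dose baseline removes a bias against the drug and brings in one that favours it, which is the more awkward direction in a single-arm open-label trial. It would also let a discretionary repeat test decide how many readings a subject's baseline contains. The Appendix D schedule, the assessment forms and the design figure are not shown in the text available, and any of them may name the reading.

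**Conclusion.** No change to the plan follows. Section 10.1 omits a detail, and the rest of the protocol points an analyst to a pre-dose FEV₁. Against a reading taken after the fall, a subject who holds steady is classified as stabilized whatever the size of the entry fall.

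The figures of −5.3% after a 10% fall and the switch to non-response at 18.2% are correct, but only if the section 2.4 average is carried into the endpoint and its pair straddles the fall. Under that reading the error is conservative in progressive-entry subjects: it can cost the drug responders and make a stage-1 futility stop more likely, but it cannot manufacture a success in that stratum. In stable-entry subjects a flat course is unaffected; only the rise needed for improvement shifts, between 7.4% and 16.1% instead of 10%.

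The effect on this trial cannot be computed, because the documents do not give the share of progressive entrants, the distribution of entry falls or the share of straddling pairs. The simulated percentages rest on assumed CVs of 3–7%. Choosing between the averaged pair and a post-fall reading is a trade-off between opposite biases on which statisticians could reasonably differ.
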